**Efficacy Analysis Set:**

All patients who meet the study entry inclusion and exclusion criteria, receive at least one dose of tenapanor during the 26-week treatment period, complete the 26-week treatment period, and achieve at least a 1.2 mg/dL reduction in serum phosphorus from baseline to the end of the 26-week treatment period will be included in the efficacy analysis set. The efficacy analysis set will be used for the primary efficacy analysis.

**Per-Protocol Analysis Set:**

All patients in the ITT analysis set who complete the 12-week randomized withdrawal period as planned with no major protocol deviations that impact the primary efficacy variable. The per-protocol (PP) analysis set will be used for sensitivity analyses to support the primary and key secondary efficacy analyses. Patients in the PP analysis set will be determined prior to the database lock or unblinding of the study data.

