**Per-Protocol (PP) Analysis Set (12-week randomized withdrawal period):**

All patients in the ITT analysis set who completed the 12-week randomized withdrawal period as planned with no major protocol deviations that impact the primary efficacy variable. The PP analysis set will be used for sensitivity analyses to support the primary and key secondary efficacy analyses.

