- d AEs and SAEs will be collected from consenting to the end of study.
- e Kt/V should be the most recent historical value prior to screening.
- f Height will also be measured at the screening visit
- g In the randomized withdrawal period, patients in the tenapanor group only are randomized 1:1 to either stay on current treatment of tenapanor or receive a matched placebo; based on withdrawal criteria, patients may enter the safety assessment period at any visit.
- h If the laboratory evaluations from the wash-out period deem the patient ineligible for the study, the site must inform the patient and tell them to take their phosphate binders.
- i s-Phosphorus sample collected at visits when safety labs are not collected.
- j KDQoL (KDQoL™-36), Kidney Disease and Quality of Life survey. DSI, Dialysis Symptom Index survey is for English speakers only and is not validated in other languages.
- k Randomization #1 is 3:1, tenapanor: active control. Randomization #2 is 1:1 from the tenapanor group only to tenapanor: placebo. Patients in the active control group will receive sevelamer carbonate for the entire 52-week study period.
- l Drug accountability will be performed for both tenapanor and the active control.
- m Visits 14, 16 and 18 are not done for subjects randomized into the active control group.
- n Patients should be randomized by the week after meeting s-P washout criteria; total period off binder must not be greater than 4 weeks.

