Patients who meet all the inclusion/exclusion criteria will be randomized 3:1 to either receive tenapanor at a dose of 30 mg bid or sevelamer carbonate based on package insert instructions (standard of care) after Visits 2, 3 or 4 (after 1, 2 or 3 weeks of wash-out) if they have a s-P level of at least 6.0 mg/dL and not more than 10.0 mg/dL and have an increase in s-P of at least 1.5 mg/dL versus pre wash-out (Visit 1, Screening visit).

Patients randomized into the tenapanor group will receive tenapanor at a dose of 30 mg bid. Tenapanor will be taken twice daily; just prior to breakfast and dinner. Patients on HD should **not** take tenapanor at the meal immediately preceding dialysis; in this case, patients will take tenapanor prior to the next meal after dialysis. Those randomized into the active control group will take sevelamer carbonate based on standard of care using the package insert for guidance for the entire 52-week study period. Patients who are on active control will **not** have Visits 14, 16 and 18.

Investigators may decrease or increase the dose of tenapanor based on s-P levels and/or GI tolerability. The changes must be made in 10 mg increments to a minimum of 10 mg bid or a maximum of 30 mg bid from enrollment until Day 183 (Visit 13). The dose of sevelamer carbonate may be adjusted based on standard of care for the entire 52-week study period.

During the 26-week treatment period and the safety extension period, patients on tenapanor with a s-P  $\geq$  10 mg/dL at any time after Week 2 of treatment or patients with a s-P  $\geq$  9 mg/dL for two consecutive visits after Week 2 will be discontinued and all visit procedures for Visit 23 will be completed, if possible. Patients in the active control group, receiving sevelamer carbonate do not have specific discontinuation criteria; they will be treated based on standard of care using the package insert for guidance.

At the end of the 26-week treatment period, patients in the tenapanor group only will be randomized 1:1 to either remain on the tenapanor dose they are taking on Day 183 (Visit 13) or receive placebo for up to an additional 12 weeks (randomized withdrawal period). During the randomized withdrawal period, patients with a s-P  $\geq$  9 mg/dL will be discontinued and all visit procedures for Visit 23 will be completed, if possible. Patients who discontinue from the

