randomized withdrawal period with s-P  $\geq$  9 mg/dL will be offered the opportunity to enter the safety extension period.

Patients who randomize into the tenapanor group and complete the randomized withdrawal period are eligible to enroll in the open label safety extension period for an additional 14 weeks. Patients who enroll in the open label safety period will receive tenapanor during this period.

Laboratory efficacy endpoints will be assessed at various times throughout the study; s-P will be measured at every visit.

Safety assessments will be performed during the study and will include physical examination, vital signs (BP/P), body weights, clinical laboratory evaluations, 12-lead electrocardiograms (ECGs), and adverse event (AE) monitoring. Blood samples will be collected and stored, as appropriate, for the potential evaluation of exploratory biomarkers related to cardio-renal disease or bone metabolism or that may influence the response (i.e. distribution, safety, tolerability, and efficacy) to tenapanor.

Details of study assessments and the schedule of events for this study are in [Section 1.3](#).

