### 5.4 Patient Withdrawal

Patients are free to discontinue the study at any time, for any reason, and without prejudice to further treatment. The Investigator may remove a patient if, in the Investigator's judgment, continued participation would pose unacceptable risk to the patient or to the integrity of the study data. Some study specific discontinuation criteria will also apply to study participants receiving tenapanor or placebo:

- **Hypophosphatemia:** Serum phosphorus  $\leq 2.5$  mg/dL at any time.
- **Hyperphosphatemia:**
  - Serum phosphorus  $\geq 10.0$  mg/dL any time after Week 2 of the 26-week treatment period
  - Serum phosphorus  $\geq 9$  mg/dL for two consecutive visits after Week 2 during the 26-week treatment or safety extension period
  - Serum phosphorus  $\geq 9$  mg/dL during the randomized withdrawal period

Patients discontinued from the randomized withdrawal period will be offered the opportunity to enter the open-label safety assessment period or be discontinued from the study and return to standard of care.

Patients in the active control group, receiving sevelamer carbonate do not have specific discontinuation criteria; they will be treated based on standard of care using the package insert for guidance.

A patient who discontinues will always be asked about the reason(s) for discontinuation and the presence of any AEs. The Investigator will record the reason for early withdrawal in the eCRF.

If a patient discontinues the study, all visit procedures for Visit 23 will be completed, if possible.

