### **9.2 Determination of Sample Size**

Approximately five hundred sixty (560) male and female patients with end stage renal disease (ESRD) on chronic maintenance hemodialysis (HD) 3 times a week for a minimum of 3 months or peritoneal dialysis (PD) for a minimum of 6 months will be enrolled in this study. Patients will be randomized in a 3:1 ratio to receive either tenapanor (~420 patients) or active control (~140 patients). Those patients in the tenapanor group will be randomized at the end of the 26-week treatment period to enter into the randomized withdrawal period to either remain on their current dose of tenapanor or placebo in a 1:1 ratio.

For the primary efficacy analysis, a sample size of 146 patients (73 patients/group) in the 12-week randomized withdrawal period is expected to provide more than 95% power to detect a difference between tenapanor and placebo treatment in the change in serum phosphorus from the end of the 26-week treatment period to the end of the 12-week randomized withdrawal period or the endpoint visit for this period, between the tenapanor treatment and placebo. This calculation is based on a two-sample t-test with a two-sided significance level of  $\alpha=0.05$ , an assumed treatment difference of 1.0 mg/dL and a common standard deviation of 1.6 mg/dL. This sample size (560) allows for a 30% dropout rate, meaning 30% of patients will not complete the 26-week treatment period. This sample size also assumes at least 50% of patients in the tenapanor group will be considered responders in the 26-week treatment period, i.e., patients who achieves at least a 1.2 mg/dL reduction from baseline to the end of the 26-week treatment period.

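### Minor, supportive analysis only: the per-protocol set requires completion of the 12-week withdrawal period, so as worded it drops patients whom the protocol itself stops on serum phosphorus

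*Combined protocol and SAP*

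**What the plan says.** Section 9.3 admits to the PP set "All patients in the ITT analysis set who complete the 12-week randomized withdrawal period as planned with no major protocol deviations" affecting the primary variable. The Synopsis uses the same condition: "All patients in the ITT analysis set who completed the 12-week randomized withdrawal period as planned with no major protocol deviations". The purpose in Section 9.3 is that the PP "analysis set will be used for sensitivity analyses to support the primary and key secondary efficacy analyses". Membership is to be settled before database lock or unblinding.

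Other sections provide for leaving the period early on s-P:

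- Section 4.1: the sentence that begins "During the randomized withdrawal period, patients with a s-P" goes on to require discontinuation at 9 mg/dL or above.
- Section 5.4 repeats that limit for the withdrawal period and adds a lower one, 2.5 mg/dL or below at any time, for patients on tenapanor or placebo. It continues: "Patients discontinued from the randomized withdrawal period will be offered the opportunity to enter the open-label safety assessment period".
- Section 1.3, footnote g: "based on withdrawal criteria, patients may enter the safety assessment period at any visit".
- Section 4.1 gives a separate route to those who "complete the randomized withdrawal period are eligible to enroll in the open label safety extension period".

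The primary analysis (Section 9.4.3) uses the efficacy analysis set, which consists of responders, and the last s-P in the period. Neither that set nor the ITT set requires completion of the withdrawal period.

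**The concern.** Discontinuing and completing are different states in Section 4.1, each with its own route into the safety extension. A patient stopped on s-P at Visits 14 to 18 is therefore not a completer and falls outside the PP set with no protocol deviation at all. Whether a patient stays in depends on s-P after the second randomisation, which is the outcome being compared. Section 9.4.5 itself expects more placebo patients to leave early for lack of efficacy, and those are the patients whose s-P rebounds most.

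What is at stake is interpretation. A PP estimate below the primary could reflect the definition rather than any fragility of the primary result, so a disagreement between the two could not be read.

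A related gap is that PP is drawn from ITT while the primary uses responders. The text does not say whether the PP check of the primary, or of the efficacy-set dose comparisons in Section 9.4.4.1, is limited to responders.

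**Working it through.** **1. The plan's own figure.** Section 9.2 gives "a sample size of 146 patients (73 patients/group) in the 12-week randomized withdrawal period", a difference of 1.0, an SD of 1.6 and two-sided alpha of 0.05. SE = 1.6 × √(2/73) = 0.265. Power = Φ(1.0/0.265 − 1.96) = Φ(1.82) = 96.5% (96.3% with the exact noncentral t). The stated power of more than 95% is reproduced and does not depend on the PP definition.

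**2. Size of the two possible parent sets.** 560 × 0.75 = 420 on tenapanor; × 0.70 = 294 entering withdrawal, or 147 per group; × 0.50 = 147 responders, or about 73 per group. The parent set matters.

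**3. Direction, by hand.** Take one visit, normal s-P, level SD 1.6 (correlation 0.5, see step 4), tenapanor at the Visit 13 mean and placebo 1.0 higher. The upper limit is reached with probability 1 − Φ((9 − mean)/1.6) and the lower with Φ((2.5 − mean)/1.6).

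| Visit 13 mean | Arm | ≥9 | ≤2.5 | Either |
|---|---|---|---|---|
| 6.5 | tenapanor | 5.9% | 0.6% | 6.5% |
| 6.5 | placebo | 17.4% | 0.1% | 17.5% |
| 5.0 | tenapanor | 0.6% | 5.9% | 6.5% |
| 5.0 | placebo | 3.0% | 1.4% | 4.5% |

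The upper rule removes more placebo patients. With both rules, the arm that loses more depends on where s-P starts. Either way, high values leave mainly from placebo and low values mainly from tenapanor, so the means of those who remain move together.

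**4. Size, by simulation.** From Section 9.2: difference 1.0 and SD of change 1.6. Assumed, because the documents do not give them:

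- Visit 13 mean 5.0 to 6.5 mg/dL, values limited to 2.5 to 10.
- Correlation between visits 0.5 to 0.7, either constant or AR(1).
- Level SD set so that the Visit 13 to 19 change has SD 1.6 before truncation: 1.6/√(2(1−ρ)) = 1.60 to 2.07 for constant correlation, and 1.6/√(2(1−ρ⁶)) = 1.14 to 1.20 for AR(1).
- Placebo rebound immediate or gradual.
- For responders, Day 1 mean 7.5 and SD 1.1 within 6 to 10, Day 1/Visit 13 correlation 0 or 0.4, and a fall of at least 1.2.
- The true difference of 1.0 kept in both parent sets.

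Patients who first meet a limit at Visits 14 to 18 are stopped; a Visit 19 value excludes no one. ANCOVA has treatment and Visit 13 s-P, with site omitted. This gives 48 scenarios for PP drawn from ITT and 96 for PP limited to responders.

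| PP completers' difference (true 1.0) | ≥9 rule only | Both rules |
|---|---|---|
| Drawn from ITT | 0.78 to 0.99 | 0.69 to 0.97 |
| Limited to responders | 0.82 to 1.00 | 0.71 to 0.97 |

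Repeat runs move these ends by about 0.02. With both rules, more tenapanor than placebo patients were excluded in 48 of the 144 scenarios. One example (responders, mean 5.0, constant correlation 0.5, immediate rebound) excludes 21% of tenapanor and 12% of placebo patients.

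**5. What happens if the stopped patients are put back.** Last-value ANCOVA then gives about 1.02 to 1.41, because the value carried forward is the extreme one that triggered the stop. The repeated-measures model of Section 9.4.5, checked under the ≥9 rule only, gives 0.98 to 1.01 with constant correlation and 0.99 to 1.10 with AR(1).

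**6. No true effect.** If both arms have the same s-P distribution, the rules remove the same kind and share of patients from each, so the expected PP difference is zero. Under the ≥9 rule the simulated difference was −0.015 to 0.004, with rejection rates of 3.7 to 5.6%.

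**The case against.** The best defence is textual. The period is described in several places as lasting up to 12 weeks, and footnote g makes exit under the criteria part of the schedule, so completing as planned might be taken to include a mandated stop. That reading is possible, but the PP definition speaks of completing the 12-week period and no section states the exception. Two careful readers could build different sets.

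Three further objections have weight. Membership is fixed while blinded, so a decision step exists, although no rule is given for it to apply. Section 9.1 refers to a separate SAP that governs; it is not in the text available and may settle the matter. And the simulated ranges rest on inputs that the documents do not supply, so they show direction and order of magnitude, not a forecast.

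A completers set is also a legitimate choice. Labelling it as one would warn the reader, but the outcome-dependent selection would remain.

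A reader might infer that the set always removes more placebo patients. The documents do not support this once the lower limit in Section 5.4 is applied: it acts mainly on tenapanor patients and can reverse the balance.

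**Conclusion.** The point stands, as minor. As worded, the PP set excludes patients who followed the protocol to a required stop, and membership depends on the post-randomisation primary variable. Under the assumptions above, a true difference of 1.0 mg/dL appears as about 0.78 to 1.00 in the PP set with the upper rule alone and about 0.69 to 0.97 with both. At the favourable end the effect is negligible.

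A reader might go further and infer that the efficacy claim is at risk or that the PP set could lend false support. Neither follows. PP carries no alpha, the bias is toward no effect, and there is none when the arms do not differ. The last-value primary and the planned repeated-measures analysis both keep these patients. What is lost is the ability to interpret a PP result smaller than the primary.

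**What to change.** Before unblinding, and unless the separate SAP already does so:

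1. Define PP as ITT patients with no major deviation affecting s-P who either complete 12 weeks or are discontinued under the protocol's own s-P criteria.
2. Analyse this set with the repeated-measures model already specified in Section 9.4.5, alongside the ANCOVA. The ANCOVA alone would exchange a bias toward no effect for an overstatement.
3. State that the set is restricted to responders when it supports the primary and the efficacy-set dose comparisons, and is drawn from the full ITT set for the ITT key secondary analyses.

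The cost is one reworded definition, one sentence on the parent set and one additional run of an existing model. No new data are needed, and the stopping rules and conduct do not change. The drawback is that the PP ANCOVA will resemble the last-value primary and so adds little beyond it.

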#### 9.4.3 Primary Efficacy Analysis

The primary efficacy variable is the change in s-P from the end of the 26-week treatment period (Visit 13) to the end of the 12-week randomized withdrawal period (Visit 19) or the endpoint visit for this period. An endpoint visit is defined as the last visit with an s-P assessment during the randomized withdrawal period. The primary interest of this study is the difference between the tenapanor treatment and placebo treatment group in the mean change (w.r.t. the primary efficacy variable) in the responder population (the efficacy analysis set). A responder is a patient that had a serum phosphorus decrease of  $\geq 1.2$  mg/dL from enrollment (Day 1) to the end of the 26-week treatment period (Visit 13). The primary efficacy variable will be analyzed using an ANCOVA model. The model includes fixed effects for treatment, pooled investigator site, and the baseline s-P value as a continuous covariate. The baseline for this analysis is defined as the s-P value at the end of 26-week treatment period. Within the framework of this model, the difference between the tenapanor treatment and placebo treatment in the mean change from the end of the 26-week treatment period to the end of the 12-week randomized withdrawal period (or the endpoint visit for this period) will be estimated. The corresponding two-sided 95% CI and the p-value for the treatment difference will also be presented. Statistical significance will be declared if the estimated difference between the tenapanor treatment and placebo treatment in the mean change is negative (i.e.,  $< 0$ ) and the corresponding two-sided p-value is  $\leq 0.05$ .

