#### 9.4.4 Secondary Efficacy Analyses

##### 9.4.4.1 Key Secondary Efficacy Analyses

The analysis method described for the primary efficacy variable in [Section 9.4.3](#) will be performed as follows:

- in the ITT analysis set
- to compare the individual doses of tenapanor and placebo in the ITT analysis set – from high dose to low dose
- to compare the individual doses of tenapanor and placebo in the efficacy analysis set – from high dose to low dose

A sequential testing procedure will be used to control the family-wise type I error rate associated with the key secondary efficacy analyses. Specifically, the primary efficacy analysis will be performed at the 5% significance level. If statistical significance is declared for this analysis, then the first key secondary efficacy analysis listed in this section will be performed at the 5% level. If statistical significance is declared for this analysis, then the next key secondary efficacy analysis will be performed at the 5% level. This procedure continues until one of the key secondary efficacy analysis in the list results in a p-value >5%. Statistical significance will be declared for secondary efficacy analyses up to this point in the list.

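### The per-protocol set named as support for the primary analysis has no responder condition, so up to about half of it could lie outside the primary population

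*Combined protocol and SAP*

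**What the plan says.** Protocol section 9.3 and the Synopsis define the PP set in nearly the same words. Section 9.3 has: "All patients in the ITT analysis set who complete the 12-week randomized withdrawal period as planned with no major protocol deviations", limited to deviations that affect the primary variable. The set "will be used for sensitivity analyses to support the primary and key secondary efficacy analyses", and membership is to be fixed before database lock or unblinding.

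Section 9.4.3 places the primary comparison "in the responder population (the efficacy analysis set"). A responder is a patient whose serum phosphorus fell by at least 1.2 mg/dL between Day 1 and Visit 13.

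The second randomisation (sections 4.1 and 6.1.4) takes tenapanor patients at the end of week 26, without regard to response. The ITT set (section 9.3) requires eligibility, at least one dose and at least one serum phosphorus value after treatment in the period, and has no responder condition either.

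The key secondary analyses (section 9.4.4.1) are, in order: the primary comparison in the ITT set, dose comparisons in the ITT set, and dose comparisons in the efficacy analysis set.

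Section 9.2 "assumes at least 50% of patients in the tenapanor group will be considered responders in the 26-week treatment period".

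**The concern.** A PP analysis in support of a primary analysis is useful when it keeps the question and the population and changes only how strictly the protocol was followed. Here the PP set is nested in the ITT set and not in the efficacy analysis set. Run as written beside the primary analysis, it makes two changes at once: it imposes completion and freedom from major deviations, and it brings in patients whom the primary analysis excludes.

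This blurs interpretation in both directions. A PP estimate smaller than the primary could be read as fragility under protocol deviations when it only reflects a wider population. A PP estimate close to the primary would not show that the responder result is robust to deviations among responders. The same mismatch affects the key secondary dose comparisons in the efficacy analysis set.

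**Working it through.** **Inputs from section 9.2.** 560 patients randomised 3:1; 30% not completing 26 weeks; at least 50% responders; 73 per group; "an assumed treatment difference of 1.0 mg/dL and a common standard deviation of 1.6 mg/dL"; two-sided alpha 0.05.

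**1. The plan's own figures.**
- Power for 73 per group, normal approximation: 1.0 / (1.6 × √(2/73)) = 3.78; Φ(3.78 − 1.96) = 96.5%. The noncentral t with 144 degrees of freedom gives 96.3%. Both agree with the statement that the sample size "is expected to provide more than 95% power to detect a difference between tenapanor and placebo treatment".
- Flow: 560 × 0.75 = 420 on tenapanor; 420 × 0.70 = 294 entering the withdrawal period; 294 × 0.50 = 147 responders, against 146 stated.

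The plan's arithmetic thus treats the 50% as a share of those completing 26 weeks.

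**2. Non-responders among patients entering the withdrawal period.**
- At the floor of 50% responders: 294 − 147 = 147, or 50%.
- At 60% responders: 40%. At 70%: 30%.
- If the 50% is taken literally as a share of all 420 tenapanor patients: 210 responders, (294 − 210) / 294 = 29%. This reading does not reproduce 146.

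**3. Effect of the completion requirement.** The documents give no completion rates to week 12, so these are assumptions. With 50% responders at entry, the PP non-responder share is c_N / (c_R + c_N), where c_R and c_N are the completion rates of responders and non-responders.

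| c_R | c_N | Non-responder share of PP set |
|---|---|---|
| 85% | 85% | 50% |
| 85% | 70% | 45% |
| 85% | 60% | 41% |
| 90% | 50% | 36% |

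**4. What the mixture does to the estimate.** Let s be the non-responder share and d the non-responder effect. The documents give no value for d, so 0, 0.3 and 0.5 mg/dL are assumed. With the planned 1.0 mg/dL in responders, the same s in both arms and no effect of deviations or of selection by completion:

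PP effect = 1.0 − s × (1.0 − d)

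| s | d = 0 | d = 0.3 | d = 0.5 |
|---|---|---|---|
| 50% | 0.50 | 0.65 | 0.75 |
| 36% | 0.64 | 0.75 | 0.82 |
| 30% | 0.70 | 0.79 | 0.85 |

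The estimate is 15-50% below 1.0 from the mixture alone. If d were also 1.0, there would be no gap.

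**5. Size of a responder-only PP set.** The ceiling is 147. At an assumed 90%, 80% or 70% completing without major deviation, n is about 132, 118 or 103. Power for 1.0 mg/dL with SD 1.6 is then about 94.9%, 92.3% or 88.7%.

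**The case against.** Five counter-arguments deserve weight.

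- **The text may be open and not wrong.** Section 9.3 does not say that the PP set replaces the efficacy analysis set, and a statistician might take the PP version of a responder analysis to mean responders who also meet the PP conditions. Section 9.1 says that a separate SAP governs; its text is not included in the document, so a restriction there cannot be ruled out. This limits certainty. But the protocol defines the set twice without a responder condition, and no section says that the two sets will be intersected.
- **The ITT parent is right for part of the job.** For the ITT key secondary analyses, an ITT-based PP set is the proper match. This stands, and the fix keeps it.
- **Other analyses help the reader.** Setting PP beside ITT holds the base population fixed, ITT beside the efficacy set shows the effect of the responder restriction, and section 9.4.5 adds an MMRM analysis in support of the primary. A reader might infer that the PP result would be uninterpretable; the documents do not support that. What is missing is a direct check of deviations within responders.
- **Completion is itself a problem.** It follows randomisation and depends partly on the outcome: sections 4.1 and 5.4 discontinue patients from the withdrawal period on a serum phosphorus threshold, and section 9.4.5 expects more early placebo dropout for lack of efficacy. A responder-only PP set keeps this weakness and would not isolate adherence either.
- **No decision rests on the PP set.** It carries no alpha and has no part in the sample size. This also stands.

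**Conclusion.** The mismatch is real and worth correcting, but its consequence is limited to the reading of a supportive analysis. As defined, the PP set is not a subset of the primary population, so a difference between the PP and primary estimates could not be attributed to protocol deviations alone.

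The size should be stated with care. A reader might infer that half of the PP set will be non-responders. Section 9.2 does not say so: 50% responders is a minimum, the 147 of 294 refers to patients entering the period, and completion may remove more non-responders than responders. Up to about half, and possibly fewer, is the supportable wording. The range of 0.50-0.85 mg/dL illustrates assumed shares and effects; it is neither a forecast nor a bound.

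Nor should non-responders be taken as patients in whom the drug never worked. The label depends on one change, Day 1 to Visit 13, so a fall of 1.1 mg/dL, or a larger fall at an earlier visit that was not sustained, also counts as non-response.

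Finally, nothing here weakens the primary test. Its population, significance level and power of more than 95% do not depend on the PP set.

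**What to change.** In section 9.3 and the Synopsis, and in the SAP if it does not already do so, replace the single PP set with two:

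- **PP-efficacy set:** patients in the efficacy analysis set who meet the PP conditions, to support the primary analysis and the dose comparisons in the efficacy analysis set.
- **PP-ITT set:** patients in the ITT set who meet the PP conditions, to support the ITT key secondary analysis and the dose comparisons in the ITT set.

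Fix both memberships before lock or unblinding, as section 9.3 already requires for the single set. Add a sentence saying that both sets condition on completion, a post-randomisation event partly driven by the outcome, and are therefore supportive only.

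The cost is a short text change and one more flag in the analysis data; no new data are needed. The downside is a smaller set behind the primary, about 103-132 patients at an assumed 70-90% completing without major deviation, which is still enough to be informative.
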